### Study Day and Visit Window

Week	Target Day a	Study Day Interval a
1	7	2-10
2	14	11-17
3	21	18-24
4	28	25-31
5	35	32-38
6	42	39-45
7	49	46-52
8	56	53-59
9	63	60-66
10	70	67-73
11	77	74-80
12	84	81-91 b

a Relative to the first day of IMP in the double blind treatment period.

CCI [REDACTED]

### 10.2 Pooling of small centers

Primary efficacy analysis will be performed on the ITT Efficacy Sample which comprises those subjects in the Randomized Sample who have a baseline value and at least one post-randomization value for CMAI Total Score in the double blind treatment period.

CCI [REDACTED]

CCI [REDACTED]

### 10.3 Scales: Rules for Scoring and Handling of Missing Data

#### 10.3.1 Cohen-Mansfield Agitation Inventory (CMAI)

The CMAI consists of 29 items all rated on a 1 to 7 scale with 1 being the “best” rating and 7 being the “worst” rating. The CMAI Total Score is the sum of ratings for all 29 items. The possible total scores are from 29 to 203. The CMAI Total Score will be unevaluable if less than 24 of the 29 items are recorded. If 24 to 28 of the 29 items are recorded, the total score will be the mean of the recorded items multiplied by 29 and then rounded to the first decimal place.

CCI [REDACTED]

[REDACTED]

[REDACTED]

[REDACTED]

[REDACTED]

#### 10.3.2 Clinical Global Impression-Severity of Illness Scale (CGI-S)

The severity of agitation for each subject will be rated using the CGI-S. To perform this assessment, the investigator (or designee) will answer the following question: “Considering your total clinical experience with this particular population, how mentally ill (as related to agitation) is the subject at this time?” Response choices are 0 = not assessed; 1 = normal, not at all ill; 2 = borderline mentally ill; 3 = mildly ill; 4 = moderately ill; 5 = markedly ill; 6 = severely ill; and 7 = among the most extremely ill

subjects. The score 0 (= not assessed) will be set to missing. The CGI-S is therefore a 7-point scale from 1 through 7.

**10.3.3** CCI [Redacted]

[Redacted]

**10.3.4** CCI [Redacted]

[Redacted]

**10.3.5 Neuro-psychiatric Inventory**

The NPI consists of 12 items. For each item there is a screening question to determine if the behavioral change is present (rated 1) or absent (rated 0). For each item there are three scores: frequency, severity, and caregiver distress (NPI/NPI-NH) or occupational disruptiveness (NPI-NH). Frequency is rated on a 1 to 4 scale, severity is rated on a 1 to 3 scale and the caregiver distress is rated on a 0 to 5 scale. The individual item score is calculated as presence x frequency x severity and has a range from 0 to 12. If presence is zero, the individual item score and caregiver distress score will be set to zero. For all items, low scores are 'better' than high scores.

CCI [Redacted]

[Redacted]

10.3.8 CCI [Redacted]

[Redacted]

[Redacted]

- | [Redacted]
- | [Redacted]
- | [Redacted]
- | [Redacted]
- | [Redacted]
- | [Redacted]

[Redacted]

### **10.3.9 National Institute of Neurological and Communicative Disorders and Stroke and the Alzheimer's Disease and Related Disorders Association (NINCDS-ADRDA)**

The NINCDS-ADRDA, which has shown good reliability and validity, provides criteria for the possible and probable diagnosis of Alzheimer's disease. These criteria require that cognitive impairment and a suspected dementia syndrome be confirmed by neuropsychological testing for a clinical diagnosis of Alzheimer's disease. The NINCDS-ADRDA criteria specify 8 cognitive domains that may be impaired in Alzheimer's disease: memory, language, perceptual skills, attention, constructive abilities, orientation, problem solving and functional abilities.

### **10.3.10 Hachinski Ischemic Scale (Rosen Modification)**

The Rosen-modified Hachinski Ischemic Scale assesses whether a subject's dementia is likely due to vascular causes by the response to 8 questions: abrupt onset, stepwise deterioration, somatic complaints, emotional incontinence, history of hypertension, history of stroke, focal neurologic signs, and focal neurologic symptoms. The Rosen modified Hachinski Ischemic Scale will be completed to assess eligibility for the trial by the same neurologist who performs the neurological examination.

### **10.3.11** CCI [REDACTED]

[REDACTED]

### **10.3.12** CCI [REDACTED]

[REDACTED]

missing items could contribute more than 6 points to the total score then the total score will be set to missing. Otherwise a mean non-missing items score will be calculated by summing the non-missing items and dividing them by the maximum score possible from the non-missing items. For missing items with possible scores from 0 to 1, the mean score will be imputed for each missing item. If item 14 is missing, two times this mean will be imputed for item 14. If items 11, 13, or 16 are missing three times this mean for will be imputed each missing item. If item 12 is missing 5 times then this mean will be imputed for item 12. After all by-item imputation has been done, the individual item scores will be added and this sum will be rounded to the first decimal place to arrive at an imputed total score. In other terms, the MMSE Total Score is simply the mean non-missing items score multiplied by 30, and then rounded to the first decimal place.

## 12 Potential Clinical Relevance Criteria from Protocol

### Appendix 1 Criteria for Identifying Laboratory Values of Potential Clinical Relevance

Laboratory Tests	Criteria
Chemistry	
AST (SGOT)	≥ 3 x upper limit of normal (ULN)
ALT (SGPT)	≥ 3 x ULN
Alkaline phosphatase	≥ 3 x ULN
LDH	≥ 3 x ULN
BUN	≥ 30 mg/dL
Creatinine	≥ 2.0 mg/dL
Uric Acid	
Men	≥ 10.5 mg/dL
Women	≥ 8.5 mg/dL
Bilirubin (total)	≥ 2.0 mg/dL
CPK	≥ 3 x ULN
Prolactin	> ULN
Hematology	
Hematocrit	
Men	≤ 37 % and decrease of ≥ 3 percentage points from Baseline
Women	≤ 32 % and decrease of ≥ 3 percentage points from Baseline
Hemoglobin	
Men	≤ 11.5 g/dL
Women	≤ 9.5 g/dL
White blood count	≤ 2,800/ mm  or ≥ 16,000/ mm 
Eosinophils	≥ 10%
Neutrophils	≤ 15%
Absolute neutrophil count	≤ 1,000/ mm 
Platelet count	≤ 75,000/ mm  or ≥ 700,000/ mm 
Urinalysis	
Protein	Increase of ≥ 2 units
Glucose	Increase of ≥ 2 units
Casts	Increase of ≥ 2 units
Additional Criteria	
Chloride	≤ 90 mEq/L or ≥ 118 mEq/L
Potassium	≤ 2.5 mEq/L or ≥ 6.5 mEq/L
Sodium	≤ 126 mEq/L or ≥ 156 mEq/L
Calcium	≤ 8.2 mg/dL or ≥ 12 mg/dL
Glucose	
Fasting	≥ 100 mg/dL
Non-Fasting	≥ 200 mg/dL
Total Cholesterol, Fasting	≥ 240 mg/dL
LDL Cholesterol, Fasting	≥ 160 mg/dL
HDL Cholesterol, Fasting	
Men	< 40 mg/dL
Women	< 50 mg/dL

Laboratory Tests	Criteria
Triglycerides, Fasting	$\geq 150$ mg/dL

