18.	
Subjects with abnormal laboratory tests results, vital signs results, or ECG findings, unless, based on the investigator's judgment, the findings are not medically significant and would not impact the safety of the subject or the interpretation of the trial results. The medical monitor should be contacted to discuss individual cases, as needed. Criteria are provided in Appendix 3, Appendix 4, and Appendix 5 to assist investigators in their assessments of results that may be potentially medically significant, depending on the subject's medical history and clinical presentation.
 
In addition, subjects with the following laboratory test and ECG results at screening must be excluded from the trial:
 
 
• Platelets <math>\leq 75,000/\text{mm}^3</math>
 
• Hemoglobin <math>\leq 9 \text{ g/dL}</math>
 
• Neutrophils, absolute <math>\leq 1000/\text{mm}^3</math>
 
• Aspartate transaminase (AST) <math>> 2 \times \text{ULN}</math>
 
• Alanine transaminase (ALT) <math>> 2 \times \text{ULN}</math>
 
• Creatine phosphokinase (CPK) <math>> 3 \times \text{ULN}</math>, unless discussed with and approved by the medical monitor
 
• Albumin <math>< 3 \text{ g/dL}</math>
 
• HbA1c <math>\geq 8\%</math>
 
• Abnormal T4, unless discussed with and approved by the medical monitor. (Note: Free T4 is measured only if the result for thyroid-stimulating hormone [TSH] is abnormal.)
 
• QTcF <math>\geq 450 \text{ msec}</math> in men and <math>\geq 470 \text{ msec}</math> in women (see Section 3.7.4.4 for further details), unless due to ventricular pacing
 
 
Tests with exclusionary results should be repeated (if ECG, 3 consecutive recordings) to ensure reproducibility of the abnormality before excluding a subject based on the criteria noted above.

Sex and Reproductive Status	

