ACTH = adrenocorticotropic hormone; ALP = alkaline phosphatase; ALT (SGPT) = alanine transaminase (serum glutamic-pyruvic transaminase); anti-HCV = hepatitis C antibodies; aPTT = activated partial thromboplastin time; AST (SGOT) = aspartate transaminase (serum glutamic-oxaloacetic transaminase); BUN = blood urea nitrogen; CPK = creatine phosphokinase; eGFR = estimated glomerular filtration rate; GGT = gamma glutamyl transferase; HbA1c = glycosylated hemoglobin; HBsAg = hepatitis B surface antigen; HDL = high density lipoprotein; IDDM = insulin-dependent diabetes mellitus; INR = International Normalized Ratio; LDH = lactic dehydrogenase; LDL = low density lipoprotein; PT = prothrombin time; RBC = red blood cell; T4 = thyroxine; TSH = thyroid-stimulating hormone; WBC = white blood cell.

aAll positive urine pregnancy test results must be confirmed by a serum test. Subjects with a positive serum pregnancy test result at screening must not be enrolled and subjects with a positive serum pregnancy test result during the trial must discontinue treatment and be withdrawn from the trial.

Protocol 331-12-284

Any value outside the normal range will be flagged for the attention of the investigator, who must indicate whether or not a flagged value is of clinical significance. If one or more values are questionable, the test(s) may be repeated. If the result of any test (or repeat test, if done) is indicated as clinically significant in the samples taken during the screening period, the subject will NOT be enrolled into the trial without the permission of the medical monitor. In addition, follow-up unscheduled laboratory tests should be performed if clinically significant abnormalities are observed. Unscheduled laboratory tests may be repeated at any time at the discretion of the investigator for appropriate medical care. Refer to [Appendix 3](#) for criteria for identifying values of potential clinical relevance.

The following laboratory test results at screening are exclusionary:

- Platelets  $\leq 75,000/\text{mm}^3$
- Hemoglobin  $\leq 9 \text{ g/dL}$
- Neutrophils, absolute  $\leq 1000/\text{mm}^3$
- Aspartate transaminase (AST)  $> 2 \times$  upper limit of normal (ULN)
- Alanine transaminase (ALT)  $> 2 \times$  ULN
- Creatine phosphokinase (CPK)  $> 3 \times$  ULN, unless discussed with and approved by the medical monitor
- Albumin  $< 3 \text{ g/dL}$
- (HbA1c  $\geq 8\%$ )

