	
22. Subjects with weight loss of more than 5% in the 7 days prior to the baseline visit or more than 10% between the screening and baseline visits.
 
23. Subjects with weight < 40 kilograms.
 
24. Subjects with dehydration or hypovolemia, or a consistent or chronic pattern of poor fluid and/or nutritional intake, or with recent need for supplemental fluid via intravenous solution or supplemental nutrition via gastric tube.
 
25. Subjects who are bedridden.
 
26. Subjects with recent clinically significant infection, as evidenced by treatment with intravenous antibiotics or hospitalization, within the 2 weeks prior to the screening visit.
 
27. Subjects who are known to be poor CYP2D6 metabolizers.
 
30. ... Tests with abnormal results should be repeated to ensure reproducibility of the abnormality before excluding a subject based on the criteria noted above. In addition, subjects with the following laboratory test and ECG results at screening must be excluded from the trial:
 
 
• Platelets <math>\leq 120,000/\text{mm}^3</math>
 
• Hemoglobin <math>\leq 10 \text{ g/dL}</math> for women, <math>11 \text{ g/dL}</math> for men
 
• Neutrophils, absolute <math>\leq 1500/\text{mm}^3</math>
 
• ...
 
• <math>\text{ACR} > 30 \text{ mg/g}</math> (calculated as urine
 
	
14. Subjects considered in poor general health based on the investigator's judgment. Examples include subjects who have a recent clinically significant weight loss, chronic dehydration or hypovolemia, poor fluid or nutritional intake, or a recent clinically significant infection, as per the investigator's judgment.
 
(this exclusion criterion was removed)
 
15. Subjects with a BMI <math>< 18.5 \text{ kg/m}^2</math>. (this exclusion criterion was removed)
 
(this exclusion criterion was removed)
 
(this exclusion criterion was removed)
 
(this exclusion criterion was removed)
 
18. ... In addition, subjects with the following laboratory test and ECG results at screening must be excluded from the trial:
 
 
• Platelets <math>\leq 75,000/\text{mm}^3</math>
 
• Hemoglobin <math>\leq 9 \text{ g/dL}</math>
 
• Neutrophils, absolute <math>\leq 1000/\text{mm}^3</math>
 
• ...
 
• QTcF <math>\geq 450 \text{ msec}</math> in men and <math>\geq 470 \text{ msec}</math> in women (see Section 3.7.4.4 for further details), unless due to ventricular pacing
 
 
Tests with exclusionary results should

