## **1 Introduction**

This statistical analysis plan (SAP) documents the statistical methodology and data analysis algorithms and conventions to be applied for statistical analysis and reporting of efficacy and safety data of study 331-12-284. All amendments to the protocol and Addendum to protocol amendment are taken into consideration in developing this SAP.

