### 9.2.2 Potentially Clinically Relevant Values

In addition, the incidence of treatment-emergent potentially clinically relevant (PCR) values identified using prospectively defined criteria in Appendix 1 for laboratory tests will be summarized by treatment group. A listing of PCRs by subject and by test will be provided.

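### The SAP's laboratory flag list claims to come from the protocol but uses a different neutrophil cut-off, and the triglyceride High shift rows drop values of 500 mg/dL and above

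*SAP*

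**What the plan says.** **Laboratory flags.** Protocol 3.7.4.2 refers the reader to its Appendix 3 "for criteria for identifying values of potential clinical relevance". In that appendix the ANC criterion is ≤1,500/mm³ and the CPK criterion is >3 × ULN. SAP section 12 carries the heading "Potential Clinical Relevance Criteria from Protocol", and its Appendix 1 gives ANC ≤1,000/mm³ and CPK ≥3 × ULN. SAP 9.2.2 makes this list operative: treatment-emergent values are identified by the "prospectively defined criteria in Appendix 1 for laboratory tests" and reported in an incidence table by treatment group and in a listing.

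**Where 1,000 appears in the protocol.** It is a screening limit. Protocol 3.7.4.2 states "The following laboratory test results at screening are exclusionary" and lists neutrophils ≤1,000/mm³. Exclusion 18 in Table 3.4.3-1 has the same limit. The Amendment 3 log shows that this eligibility limit was lowered from 1,500; its readable text shows no change to Appendix 3.

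**Triglycerides.** SAP 9.2.4 has five triglyceride rows. Three of them, for baselines normal, borderline, and normal or borderline, end in *High*, defined as 200 to below 500 mg/dL. A fourth runs from a normal baseline to ≥150 and is the only one that names *Very High*. The fifth counts any rise of at least 50. In the same table the *High* rows for LDL (≥160) and glucose (≥126) have no upper limit.

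**The concern.** A reader of the clinical study report would take the section 12 heading at its word and believe that the protocol's criteria had been applied. For ANC they would not have been. Protocol Appendix 3 gives investigators one threshold, and the report would count against another. In the ANC row the whole band 1,001–1,500/mm³ would be missing relative to the protocol's rule.

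The triglyceride point is independent of this. It is a gap in the SAP's own table: the most extreme shifts leave the *High* rows, while smaller ones stay in.

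Both bear on counts of outlying laboratory values, which are among the pre-specified safety outputs of the trial.

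**Working it through.** **Step 1: line-by-line comparison.** Protocol Appendix 3 and SAP Appendix 1 each contain 34 criteria, counting sex-specific and fasting or non-fasting lines separately. Thirty-two agree. The two that differ:

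| Test | Protocol Appendix 3 | SAP Appendix 1 | Values affected |
|---|---|---|---|
| ANC | ≤1,500/mm³ | ≤1,000/mm³ | 1,001 to 1,500 |
| CPK | >3 × ULN | ≥3 × ULN | exactly 3 × ULN |

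**Step 2: is the SAP value simply the amended screening limit?** Amendment 3 changed three haematology screening limits:

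| Test | Screening, before → after Amendment 3 | Protocol Appendix 3 | SAP Appendix 1 |
|---|---|---|---|
| Platelets (lower limit) | 120,000 → 75,000 | 75,000 | 75,000 |
| Haemoglobin | 10 (women), 11 (men) → 9 | 9.5 (women), 11.5 (men) | 9.5 (women), 11.5 (men) |
| ANC | 1,500 → 1,000 | 1,500 | 1,000 |

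The SAP did not take over the screening limits as a general policy, because haemoglobin stayed at the Appendix 3 values. Only ANC moved. A carry-over from eligibility is possible but not documented.

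**Step 3: do other SAP flags catch ANC 1,001–1,500?** Take ANC = WBC × neutrophil fraction. The other relevant SAP flags are WBC ≤2,800 or ≥16,000, and neutrophils ≤15%. A value escapes both when WBC is at least 2,801 and ANC/WBC > 0.15, that is, WBC < ANC/0.15.

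- ANC 1,001: 1,001/0.15 = 6,673.3, so it escapes at WBC 2,801–6,673.
- ANC 1,250: 1,250/0.15 = 8,333.3, so it escapes at WBC 2,801–8,333.
- ANC 1,500: 1,500/0.15 = 10,000, where the fraction is exactly 15% and is flagged, so it escapes at WBC 2,801–9,999.

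**Step 4: triglyceride rows.** Label the rows of SAP 9.2.4: A, <150 to 200–<500; B, 150–<200 to 200–<500; C, <200 to 200–<500; D, <150 to ≥150; E, rise ≥50. Rows A, B and C are the *High* rows.

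| Baseline → post-baseline (mg/dL) | Rows entered | *High* rows |
|---|---|---|
| 180 → 499 | B, C, E | 2 |
| 180 → 500 | E | 0 |
| 120 → 499 | A, C, D, E | 2 |
| 120 → 500 | D, E | 0 |
| 180 → 250 and 600 at two visits | B, C, E | 2 |
| 180 → 190 and 600 at two visits | E | 0 |

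So the gap applies to a subject with baseline below 200 who reaches ≥500 and has no other post-baseline fasting value at 200–<500. Such a subject has risen by more than 500 − 200 = 300, so row E always counts the change. A normal baseline also enters row D. A borderline baseline enters no categorical row.

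**Step 5: can a second visit close the gap?** Protocol Table 3.7-1 schedules post-baseline chemistry three times: Weeks 4, 8 and 12/ET. Among these visits, footnote n makes fasting mandatory only at Week 12/ET, although 3.7.1.3.2 describes the Week 4 and 8 draws as fasting. A subject who leaves before Week 4 has one scheduled post-baseline draw, so no second scheduled value exists.

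**The case against.** The strongest reply is that the SAP may set its own table threshold. Protocol 7.6 and 7.6.2 speak of prospectively defined criteria without citing Appendix 3 and leave the details of the safety analysis to the SAP. The SAP also says "All amendments to the protocol and Addendum to protocol amendment are taken into consideration", and that addendum is not among the documents, so the lower ANC value may be deliberate. This stands as far as it goes: neither value is shown to be wrong. It does not rescue the heading, which says that the criteria come from the protocol.

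A second reply is that the incidence table counts treatment-emergent values and that screening admits any ANC above 1,000. Some subjects may therefore enter already at 1,001–1,500 and, on the usual reading, would not count as new events under ≤1,500 either. That is fair, but it covers only those subjects, and the SAP does not define treatment-emergent for these flags.

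On triglycerides, an upper bound on *High* is consistent with the SAP's separate mention of *Very High*, and no affected subject disappears: row E and the ≥150 flag in SAP Appendix 1 still apply. This limits the harm. It does not explain why *Very High* has no shift row of its own, or why LDL and glucose are treated differently.

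Other safeguards also remain. Protocol 3.7.4.2 says "Any value outside the normal range will be flagged for the attention of the investigator", a change judged clinically significant is recorded as an adverse event (Protocol 5.1), and SAP 9.2.1 summarises mean change by visit. But mean changes do not count outliers, and adverse-event recording depends on judgement.

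**Conclusion.** The concern holds. The SAP's ANC flag is not the protocol's, although the heading says that it is, and the readable text gives no explanation. This is an unreconciled mismatch; the documents do not show which cut-off was intended. Its size, measured against the protocol criterion and assuming ANC = WBC × neutrophil fraction, is the band 1,001–1,500/mm³ in the ANC row, much of which the other flags do not catch. CPK is a trivial second difference.

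The triglyceride *High* rows give a perverse result under the condition in Step 4: a rise to 499 is counted and a rise to 500 is not.

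The number of subjects affected by either point cannot be computed from the documents. All the outputs concerned are descriptive safety tables; the efficacy analyses, alpha and sample size are untouched. The point should be corrected, but it does not threaten the trial's main conclusion.

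**What to change.** Before unblinding:

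1. Reconcile the ANC and CPK criteria between SAP Appendix 1 and protocol Appendix 3. If the SAP values are intended, state their source and reword the section 12 heading. Tabulating ANC at both cut-offs is an option.
2. Define the three triglyceride *High* rows as ≥200, or add a shift row to ≥500 for each baseline category.
3. As a minor clarification in the same section, say how baseline enters the treatment-emergent metabolic syndrome definition. The footnote gives the source of the baseline value but not its use.

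The cost is a few table edits and one heading or source note in the SAP. No new data are needed. Making the change before unblinding avoids altering safety cut-offs after results are known.

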## Appendix 2                      Criteria for Identifying Vital Signs of Potential Clinical Relevance

Variable	Criterion Value a	Change Relative to Baseline a
Heart Rate b	> 120 bpm < 50 bpm	≥ 15 bpm increase ≥ 15 bpm decrease
Systolic Blood Pressure b	> 180 mmHg < 90 mmHg	≥ 20 mmHg increase ≥ 20 mmHg decrease
Diastolic Blood Pressure b	> 105 mmHg < 50 mmHg	≥ 15 mmHg increase ≥ 15 mmHg decrease
Orthostatic Hypotension	≥ 20 mmHg decrease in systolic blood pressure and a ≥ 25 bpm increase in heart rate from supine to sitting/standing	Not Applicable (baseline status not considered)
Weight	-	≥ 7% increase ≥ 7% decrease

a In order to be identified as potentially clinically relevant, an on-treatment value must meet the “Criterion Value” and also represent a change from the subject’s baseline value of at least the magnitude shown in the “Change Relative to Baseline” column.

b As defined in “Supplementary Suggestions for Preparing an Integrated Summary of Safety Information in an Original NDA Submission and for Organizing Information in Periodic Safety Updates,” FDA Division of Neuropharmacological Drug Products draft (2/27/87).

### Appendix 3 Criteria for Identifying ECG Measurements of Potential Clinical Relevance

Variable	Criterion Value a	Change Relative to Baseline a
Rate		
Tachycardia	≥ 120 bpm	increase of ≥ 15 bpm
Bradycardia	≤ 50 bpm	decrease of ≥ 15 bpm
Rhythm		
Sinus tachycardia b	≥ 120 bpm	increase of ≥ 15 bpm
Sinus bradycardia c	≤ 50 bpm	decrease of ≥ 15 bpm
Supraventricular premature beat	all	not present → present
Ventricular premature beat	all	not present → present
Supraventricular tachycardia	all	not present → present
Ventricular tachycardia	all	not present → present
Atrial fibrillation	all	not present → present
Atrial flutter	all	not present → present
Conduction		
1° atrioventricular block	PR ≥ 200 msec	increase of ≥ 50 msec
2° atrioventricular block	all	not present → present
3° atrioventricular block	all	not present → present
Left bundle-branch block	all	not present → present
Right bundle-branch block	all	not present → present
Pre-excitation syndrome	all	not present → present
Other intraventricular conduction block d	QRS ≥ 120 msec	increase of ≥ 20 msec
Infarction		
Acute or subacute	all	not present → present
Old	all	not present → present ≥ 12 weeks post study entry
ST/T Morphological		
Myocardial Ischemia	all	not present → present
Symmetrical T-wave inversion	all	not present → present
Increase in QTc	QTcF ≥ 450 msec (men) QTcF ≥ 470 msec (women)	

a In order to be identified as potentially clinically relevant, an on-treatment value must meet the “Criterion Value” and also represent a change from the subject’s baseline value of at least the magnitude shown in the “Change Relative to Baseline” column.

b No current diagnosis of supraventricular tachycardia, ventricular tachycardia, atrial fibrillation, atrial flutter, or other rhythm abnormality.

c No current diagnosis of atrial fibrillation, atrial flutter, or other rhythm abnormality.

d No current diagnosis of left bundle branch block or right bundle branch block.

CCI

CCI

CCI

CCI

CCI

CCI

CCI

CCI

